**IMGN901: IV**

Days: 1 and 8

Dose: 110 mg/m^2/dose

Administer IMGN901 IV infusion within 8 hours of preparation using a low protein binding 0.22-micron filter.

Administer at a rate of 0.02 mg/kg/min (maximum 1 mg/min) for the first 15 minutes. Provided the patient tolerates this rate, the rate can be increased to 0.06 mg/kg/min (maximum 3 mg/min). If the patient tolerates Cycle 1 Day 1 infusion, all subsequent infusions may be delivered at the 0.06 mg/kg/min (maximum 3 mg/min) rate. The administration of the study drug is approximately 1-1.5 hours in duration and will vary slightly depending on the dose. The table below provides examples of infusion rate calculations.

If an infusional reaction occurs, the infusion should be stopped and supportive care given as per institutional guidelines. Anaphylactic precautions should be observed during IMGN901 administration. Patients should be monitored for at least 1 hour after completion of the infusion. See [Section 5.4.4](#) for management and dose modification guidelines for infusional reactions.

Drug doses should be adjusted based on the BSA calculated from height and weight measured within 7 days prior to the beginning of each cycle.

Note: Pretreatment use of acetaminophen and/or diphenhydramine may be considered as per Investigator's routine practice. If provided, it is recommended that these agents be administered 30 to 60 minutes prior to the start of the IMGN901 infusion.

**IMGN901 Infusion Rate Calculation Examples Cycle 1 (Dose Level 1 (110 mg/m^2/dose))**

Example #	Patient demographics	Initial fusion rate (0.02 mg/kg/min)	Subsequent infusion rate (0.06 mg/kg/min)	Total Infusion Duration
1	Weight – 12 kg BSA – 0.52 m  IMGN901 dose = 57 mg	0.02 mg/kg/min x 12 kg = 0.24 mg/min x 15 min = 3.6 mg  (3.6 mg of IMGN901 delivered over initial 15 min, with 53.4 mg remaining)	0.06 mg/kg/min x 12 kg = 0.72 mg/min  53.4 mg : 0.72 mg/min = 74.2 min  (remaining 53.4 mg of IMGN901 delivered over 74.2 min)	15 min + 74.2 min = 89.2 min
2	Weight – 30 kg BSA – 1.1 m  IMGN901 dose = 121 mg	0.02 mg/kg/min x 30 kg = 0.6 mg/min x 15 min = 9 mg  (9 mg of IMGN901 delivered over initial 15 min, with 112 mg remaining)	0.06 mg/kg/min x 30 kg = 1.8 mg/min  112 mg : 1.8 mg/min = 62.2 min  (remaining 112 mg of IMGN901 delivered over 62.2 min)	15 min + 62.2 min = 77.2 min

3	Weight – 77 kg BSA – 1.92 m  IMGN901 dose = 211 mg	0.02 mg/kg/min x 77 kg = 1 mg/min (max rate) x 15 min = 15 mg  (15 mg of IMGN901 delivered over initial 15 min, with 196 mg remaining)	0.06 mg/kg/min x 77 kg = 3 mg/min (max rate)  196 mg : 3 mg/min = 65.3 min  (remaining 196 mg of IMGN901 delivered over 65.3 min)	15 min + 65.3 min = 80.3 min
----------	--	--	---	--

**Dexamethasone: PO or IV**

Days: 0 and 7

Dose: 4 mg/m^2/dose (max dose 10 mg) BID (i.e., total daily dose = 8 mg/m^2/day)

On the day prior to administration of IMGN901, patients should receive dexamethasone twice a day (BID). The administration of dexamethasone BID 1 day prior to IMGN901 in patients with diabetes may be omitted at the discretion of the Investigator. Additionally, modifications in dexamethasone dosing such as the elimination or reduction of doses may be taken if a patient is shown to be intolerant of full dosing.

**Dexamethasone: IV**

Days: 1 and 8

Dose: 4 mg/m^2/dose (max dose 10 mg)

On the day of infusion, patients should receive dexamethasone approximately one hour prior to the first chemotherapy infusion.

See [Section 5.0](#) for Dose Modifications based on Toxicities, including specific criteria for Day 8 IMGN901 infusions.

Following completion of Cycle 1, the next cycle starts on Day 22 or when patient has again met laboratory parameters as defined in eligibility [Section 3.2.5](#) (whichever occurs later).

**4.3 Therapy Subsequent to Cycle 1 (Cycles 2-17)**

4.3.1 Therapy Delivery Map – Cycles 2-17                  This therapy delivery map (TDM) relates to all cycles given after Cycle 1. Each cycle lasts 21 days. Patient may receive additional cycles if they meet the requirements described in Section 4.1.3. Cycles may be repeated for up to 17 cycles of therapy in total, up to a total duration of therapy of 12 months, absent disease progression or unacceptable toxicity.
	_____ Patient COG ID number
	_____ DOB

See [Section 4.1.3](#) for guidelines for starting next cycle. Extensive details are [Section 4.3.3](#). This TDM is on 1 page.

DRUG	ROUTE	DOSAGE	DAYS	IMPORTANT NOTES
IMGN901 IND # 126953	IV 0.06 mg/kg/min (maximum 3 mg/min)*	110 mg/m  (dose level 1). See Dose Schema in Section 4.1.4	1 and 8	*unless patient did not tolerate Cycle 1 Day 1 infusion (see Section 4.2.3 ). The administration of the study drug is approximately 1-1.5 hours in duration and will vary slightly depending on the dose.
Dexamethasone	PO/IV	4 mg/m  /dose (max 10 mg) BID	0 and 7	Total daily dose: 8 mg/m  /day
Dexamethasone	IV	4 mg/m  /dose (max dose 10 mg)	1 and 8	Administer approximately one hour prior to the first chemotherapy infusion.

Enter Cycle #: \_\_\_\_\_ Ht \_\_\_\_\_ cm Wt \_\_\_\_\_ kg BSA \_\_\_\_\_ m^2

Date Due	Date Given	Day	DEX (PO/IV) mg	DEX (IV) mg	IMGN901 mg	Studies	
Enter calculated dose above and actual dose administered below							
		0	_____ mg				
		1		_____ mg	_____ mg	a-e, g, h	
		7	_____ mg				
		8		_____ mg	_____ mg		
		15					
		21					
		Following completion of this cycle, the next cycle starts on Day 22 or when patient has again met laboratory parameters as defined in eligibility Section 3.2.5 (whichever occurs later).					f

See [Section 5.0](#) for Dose Modifications for Toxicities (including specific criteria for Day 8 IMGN901 infusions) and the COG Member website for Supportive Care Guidelines.

4.3.3 Treatment Details: Cycles 2-17

**IMGN901: IV**

Days: 1 and 8

Dose: 110 mg/m^2/dose

Administer IMGN901 IV infusion within 8 hours of preparation using a low protein binding 0.22-micron filter.

Administer at a rate of 0.06 mg/kg/min (maximum 3 mg/min) unless patient did not tolerate Cycle 1 Day 1 infusion (see Section 4.2.3). The administration of the study drug is approximately 1-1.5 hours in duration and will vary slightly depending on the dose. The table below provides examples of infusion rate calculations.

If an infusional reaction occurs, the infusion should be stopped and supportive care given as per institutional guidelines. Anaphylactic precautions should be observed during IMGN901 administration. Patients should be monitored for at least 1 hour after completion of the infusion. See Section 5.4.4 for management and dose modification guidelines for infusional reactions.

Drug doses should be adjusted based on the BSA calculated from height and weight measured within 7 days prior to the beginning of each cycle.

Note: Pretreatment use of acetaminophen and/or diphenhydramine may be considered as per Investigator's routine practice. If provided, it is recommended that these agents be administered 30 to 60 minutes prior to the start of the IMGN901 infusion.

**IMGN901 Infusion Rate Calculation Examples Cycles 2-17 (Dose Level 1 (110 mg/m^2/dose))**

Example #	Patient demographics	Infusion rate calculations (0.06 mg/kg/min)	Total Infusion Duration
1	Weight – 12 kg BSA – 0.52 m  IMGN901 dose = 57 mg	0.06 mg/kg/min x 12 kg = 0.72 mg/min  57 mg : 0.72 mg/min = 79.2 min	79.2 min
2	Weight – 30 kg BSA – 1.1 m  IMGN901 dose = 121 mg	0.06 mg/kg/min x 30 kg = 1.8 mg/min  121 mg : 1.8 mg/min = 67.2 min	67.2 min
3	Weight – 77 kg BSA – 1.92 m  IMGN901 dose = 211 mg	0.06 mg/kg/min x 77 kg = 3 mg/min (max rate)  211 mg : 3 mg/min = 70.3 min	70.3 min

**Dexamethasone: PO or IV**

Days: 0 and 7

Dose: 4 mg/m^2/dose (max dose 10 mg) BID (i.e., total daily dose = 8 mg/m^2/day)

On the day prior to administration of IMGN901, patients should receive dexamethasone twice a day (BID). The administration of dexamethasone BID 1 day prior to IMGN901 in patients with diabetes may be omitted at the discretion of the Investigator. Additionally, modifications in

dexamethasone dosing such as the elimination or reduction of doses may be taken if a patient is shown to be intolerant of full dosing.

**Dexamethasone: IV**

Days: 1 and 8

Dose: 4 mg/m^2/dose (max dose 10 mg)

On the day of infusion, patients should receive dexamethasone approximately one hour prior to the first chemotherapy infusion. Additionally, modifications in dexamethasone dosing such as the elimination or reduction of doses may be taken if a patient is shown to be intolerant of full dosing.

See [Section 5.0](#) for Dose Modifications based on Toxicities, including specific criteria for Day 8 IMG901 infusions.

Following completion of this cycle, the next cycle starts on Day 22 or when patient has again met laboratory parameters as defined in eligibility [Section 3.2.5](#) (whichever occurs later).

## 5.0 DEFINITIONS AND DOSE MODIFICATIONS FOR TOXICITY

### 5.1 Dose Modifications for Day 8 Dosing due to Toxicity on Day 8

#### 5.1.1 Hematological Toxicity (All Age Cohorts)

Patients who have Grade 4 neutropenia or platelets  $< 75,000/\mu\text{L}$  on Day 8 will have their IMG901 dose (and Day 7 and 8 dexamethasone doses if not yet given) withheld. If the toxicity resolves to  $\text{ANC} \geq 750/\mu\text{L}$  and platelets  $\geq 75,000/\mu\text{L}$  (transfusion independent) by Day 11, the dose may be given with appropriately timed dexamethasone support as is feasible and future doses should not be reduced. If the toxicity does not resolve to  $\text{ANC} \geq 750/\mu\text{L}$  and platelets  $\geq 75,000/\mu\text{L}$  by Day 11, the dose will be omitted and this will be considered a DLT. Patients should receive subsequent cycles of drug but at the next lower dose level. Patients who require that their Day 8 dose be omitted for Grade 4 neutropenia or platelets  $< 75,000/\mu\text{L}$  after an initial dose reduction should have all future Day 8 doses omitted.

Patients who meet hematological DLT criteria as defined in [Section 5.2.2](#) on Day 8 will have their Day 8 dose (and Day 7 and 8 dexamethasone doses if not yet given) omitted. Patients should receive subsequent cycles of drug but at the next lower dose level. Patients who require that their Day 8 dose be omitted for hematologic DLT as defined in [Section 5.2.2](#) after an initial dose reduction should have all future Day 8 doses omitted.

Patients who require more than 2 dose reductions must be removed from protocol therapy.

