### 3.2.5 Organ Function Requirements

#### 3.2.5.1 Adequate Bone Marrow Function Defined As:

- a. For patients with solid tumors without bone marrow involvement:
  - Peripheral absolute neutrophil count (ANC)  $\geq 1000/\mu\text{L}$
  - Platelet count  $\geq 100,000/\mu\text{L}$  (transfusion independent, defined as not receiving platelet transfusions within a 7-day period prior to enrollment)
- b. For patients with solid tumors and known bone marrow metastatic disease:
  - Peripheral absolute neutrophil count (ANC)  $\geq 750/\mu\text{L}$
  - Platelet count  $\geq 75,000/\mu\text{L}$  (transfusion independent, defined as not receiving platelet transfusions for at least 7 days prior to enrollment).

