#### 4.1.3 Criteria for Starting Subsequent Cycles

A cycle may be repeated every 21 days if the patient has at least stable disease, has again met laboratory parameters as defined in the eligibility section ([Section 3.2.5](#)) and has not met one of the Off Protocol Therapy or Off Study Criteria ([Section 8.0](#)). Patients who have experienced dose-limiting toxicity (DLT) (see

[Section 5.0](#)) in the previous cycle should have the dose modified (see [Section 4.1.4](#)). Treatment may consist of up to 17 cycles, for a total duration of therapy approximating 12 months, absent disease progression or unacceptable toxicity. To continue on therapy the patient must have at least clinically and radiographically stable disease. Radiographic disease evaluations will be done after the 2nd cycle of therapy, after every other cycle until 6 months, and then every 3 months.

4.1.4 Dose Schema:

The starting dose will be 110 mg/m^2 (dose level 1). For patients with toxicities as outlined in [Section 5.0](#) and who recover to starting criteria within 7 days as outlined in [Section 4.1.3](#), a single dose reduction to the next lowest dose level will be allowed.

Dose Level	IMGN901 (mg/m  )	Day(s) of Administration
-2	75	1 and 8
-1	90	1 and 8
1*	110	1 and 8

\*Starting dose level

Further dose reduction for toxicity will be considered if dose level -1 is not tolerated. No dose escalations will occur.

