### 5.2.2 Hematological Dose-Limiting Toxicity

5.2.2.1 Definition of a Hematological Dose-Limiting Toxicity for Patients without Bone Marrow Involvement at Enrollment

- Grade 3 thrombocytopenia occurring in conjunction with Grade 3 bleeding (CTCAE terms hemorrhage or epistaxis)
- Grade 4 neutropenia for  $> 7$  days
- Platelet count  $< 20,000/\mu\text{L}$  on 2 separate days, or requiring a platelet transfusion on 2 separate days, within a 7 day period
- Myelosuppression that causes a delay of  $\geq 14$  days between treatment cycles
- Any Grade 5 hematological toxicity.

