### 9.6 Evaluability for Toxicity

All patients who receive at least one dose of IMG901 according to protocol guidelines and either 1) experience a toxicity, or 2) complete the first cycle with no toxicity, will be considered in the evaluation of toxicity.

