## 10.5 Response Criteria for Neuroblastoma Patients with Bone Marrow Involvement

### 10.5.1 Bone Marrow Involvement

**Note:** patients with bone marrow as the ONLY site of disease are not eligible for this study. Response criteria in this section are intended to be used when assessing marrow involvement as a component of overall response.

Histologic analysis at the local institution of marrow tumor cell involvement is **required** for patients with a history of marrow involvement. Marrow aspirate and biopsy should be evaluated at baseline and every 2 cycles thereafter. Note: If progressive disease is documented by RECIST criteria using tumor measurements or by MIBG scan, then a repeat BM is not needed to confirm PD.

- Complete Response: No tumor cells detectable by routine morphology on 2 consecutive bilateral bone marrow aspirates and biopsies performed at least 3 weeks apart. Normalization of urinary catecholamines or other tumor markers if elevated at study enrollment.
- Progressive Disease:
  - Patients who enroll with neuroblastoma in bone marrow by morphology have progressive disease if there is a doubling in the amount of tumor in the marrow AND a minimum of 25% tumor in bone marrow by morphology. (For example, a patient entering with 5% tumor in marrow by morphology must increase to  $\geq 25\%$  tumor to have progressive disease; a patient entering with 30% tumor must increase to  $> 60\%$ ).
  - Patients who enroll without evidence of neuroblastoma in bone marrow will be defined as progressive disease if tumor is detected in 2 consecutive bone marrow biopsies or aspirations done at least 3 weeks apart or the treating physician determines that a single positive bone marrow indicates clinical progression of disease.
- Stable Disease: Persistence of tumor in bone marrow that does not meet the criteria for either complete response or progressive disease.

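### The DLT and dose-modification rules in Sections 4.1.4 and 5.1 to 5.4 contradict each other on recovery time, neutropenia and number of reductions, and Section 5.2 gives no single DLT definition for reporting

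*Combined protocol and SAP*

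**What the plan says.** - **Recovery window.** Section 4.1.4 allows a reduction for patients with Section 5.0 toxicities "who recover to starting criteria within 7 days", and refers to Section 4.1.3. That section opens with "A cycle may be repeated every 21 days if the patient has at least stable disease" and adds laboratory and off-therapy conditions, but no day limit. Section 5.4.1 lets a patient with a non-haematological DLT continue one level lower if laboratory entry limits are met again up to 14 days after the next cycle was due. Section 5.3.1 sends dose-limiting thrombocytopenia to the next lower level and names no window.
- **Neutropenia.** For Grade 4 neutropenia on Day 8 without recovery by Day 11, Section 5.1.1 states "this will be considered a DLT. Patients should receive subsequent cycles of drug but at the next lower dose level". Section 5.3.2 keeps the dose and adds growth factor for Grade 4 neutropenia of more than 7 days, provided there is no other DLT.
- **Number of reductions.** Section 4.1.4 allows one reduction, then says more will be considered if level -1 is not tolerated. Section 5.1 removes a patient who needs more than two. Yet under Section 5.1.1, patients whose Day 8 dose is omitted for counts "after an initial dose reduction should have all future Day 8 doses omitted"; Sections 5.3.3 and 5.4.2 do the same for a further DLT of their kind. Section 9.2 explains level -2 only for patients accrued at level -1.
- **DLT definition.** The one list in Section 5.2.2 is headed "Definition of a Hematological Dose-Limiting Toxicity for Patients without Bone Marrow Involvement at Enrollment". Section 3.2.5.1 sets separate entry limits "For patients with solid tumors and known bone marrow metastatic disease", and Section 10.5.1 says only that "patients with bone marrow as the ONLY site of disease are not eligible for this study". Section 9.6 admits treated patients who have a toxicity or "complete the first cycle with no toxicity, will be considered in the evaluation of toxicity", with no marrow exception.

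**The concern.** These are operative instructions. Two sites that each follow the text exactly could dose the same patient differently, or one could continue treatment where the other does not. Tolerability is a primary aim (1.1.2), and Section 9.2 counts any DLT as an excessive toxicity event. If the DLT definition depends on which section is read, the reported DLT count cannot be reproduced from the protocol. Section 9.1.1 plans a further 6 + 8 + 11 = 25 evaluable patients in the three primary strata, so the instructions remain in use.

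**Working it through.** The plan states no figure for these rules, so there is none to reproduce. The check sets the sections side by side.

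**(a) Recovery window.** Under Section 4.2.3 the next cycle is due on Day 22.
- Section 5.4.1 limit: 22 + 14 = Day 36.
- Section 4.1.4 limit: 7 days from an unstated day. Assuming it runs from the planned start, 22 + 7 = Day 29, and the two texts disagree for recovery on Days 30 to 36 (7 days).
- Assuming instead that it runs from onset, with onset on Day 15 for illustration, the limit is 15 + 7 = Day 22, and they disagree on Days 23 to 36 (14 days).
- The disagreement vanishes only if the 7 days begin on Day 36 - 7 = 29 or later.
- Platelets: a myelosuppression delay of 14 days or more is a DLT in Section 5.2.2.1. If it is thrombocytopenia, Section 5.3.1 sends it to the next lower level. Counted from the planned start, such a patient is ready on Day 36 at the earliest and cannot meet a Day 29 limit.

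**(b) Neutropenia.** Take Grade 4 neutropenia from Day 8 to Day 16: 9 days inclusive, 8 elapsed, more than 7 either way, and unresolved at Day 11. It meets both rules. For a patient at 110 mg/m2 the planned next cycle is:
- Section 5.1.1: 2 x 90 = 180 mg/m2.
- Section 5.3.2: 2 x 110 = 220 mg/m2.
- Difference: 220 - 180 = 40 mg/m2, with 180/220 = 82%.

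An episode unresolved at Day 11 that lasts 7 days or less, with no cycle delay over 14 days, falls under Section 5.1.1 alone. The conflict is therefore confined to overlapping episodes. On frequency, Section 2.3.1 reports a Grade 4 haematologic abnormality of any kind in 1% of 198 adults on single-agent treatment (about 2 patients). Those are adult data and do not bound the Section 5.1.1 platelet trigger.

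**(c) Number of reductions.**

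| Section | After the first reduction |
|---|---|
| 4.1.4, first statement | one reduction is the allowance |
| 4.1.4, below the table | more will be considered |
| 5.1.1, 5.1.2 | removal only when more than two are needed |
| 5.1.1, 5.3.3, 5.4.2 | all later Day 8 doses omitted |
| 9.2 | level -2 explained only for patients accrued at -1 |

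For repeated DLTs of one kind the route is one reduction, then Day 8 omission, then removal (Sections 5.3.4 and 5.4.3). A count of more than two reductions is never reached on that route, so the Section 5.1 limit needs a stated use.

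**(d) DLT definition (secondary).**
- Marrow-involved patients may enrol, but no Section 5.2.2.1 item is written for them. Section 5.1.1 has no marrow restriction, so it can assign them a haematological DLT.
- Section 5.1.1 calls Day 11 non-recovery a DLT. Section 5.2 defines DLT by its own list, which does not contain that event or refer to it.
- The cycle-delay criterion is 14 days or more in Section 5.2.2.1 and more than 14 in Section 5.3.2. The two differ only at exactly 14 days.

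**The case against.** The best defence is that a careful reader can harmonise much of this.

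- **Section 5 governs.** Section 8.1 and the therapy delivery maps send the reader to Section 5.0. But Section 4.1.3 sends patients with a DLT to Section 4.1.4 for modification, and no precedence is stated.
- **The citation of Section 4.1.3 concerns starting criteria, not the 7 days.** That is the natural reading and it stands. The 7-day condition remains, still without a start day.
- **The no-other-DLT condition in Section 5.3.2 yields to Section 5.1.1.** This is workable but not clearly intended, because the supposed other DLT is the same neutropenia. The worst-toxicity line in Section 5.1.2 ranks toxicities; it does not choose between two actions for one.
- **More than two reductions is an outer cap for DLTs of different kinds.** Section 5.4.1 makes this possible. The text does not say so, and it does not fit the single reduction in Section 4.1.4.
- **Marrow-involved patients count only for non-haematological and Section 5.1.1 events.** This is coherent but unstated.

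Stronger readings that the documents do not support:
- A reader might set 150 mg/m2 per cycle (two doses at level -2) against 90 mg/m2 (level -1 with Day 8 omitted). No rule directs that second reduction, and the Day 1 dose after omission is not stated.
- A reader might take the 11 further neuroblastoma patients as a count of marrow-involved patients. The documents give no marrow-involvement rate.
- A reader might say that marrow-involved patients have no haematological rule. Sections 5.1.1 and 5.3 carry no marrow restriction. Nor is a platelet entry floor equal to the Day 8 trigger (75,000) a defect in itself.
- A reader might compute how the first-six rule shifts when some patients cannot contribute a haematological DLT. That needs DLT rates and marrow counts that the documents do not give.

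**Conclusion.** The passages contradict each other as written and must be reconciled. Three conflicts survive the objections: 7 against 14 days for recovery, lower level against same dose for one overlapping neutropenia episode, and one reduction against a limit of more than two alongside Day 8 omission. The gaps in the DLT definition are secondary and matter for reporting.

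The size can be stated per patient, not as a trial-wide frequency. In (a), 7 calendar days are in dispute if both windows run from Day 22. In (b), 40 mg/m2 of planned dose in the next cycle is in dispute for a patient at 110 mg/m2, probably in few patients. For (c) and (d) the documents support no number.

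A reader might infer that the dose decision itself is compromised. It appears already complete: Section 7.2.1 speaks of the first six patients in the past tense, Section 9.1.1 counts 10 + 8 + 5 = 23 primary-stratum patients enrolled before Amendment #1, and 110 mg/m2 is still the starting dose. For that decision the need is only to say which definition was used. The Bayesian neuropathy rule uses Grade 3 or higher neuropathy, and the response endpoint uses centrally reviewed response; neither is affected. Section 9.2 sets no action threshold on DLTs in general after the first-six rule, so the consequence is consistency of treatment and reporting.

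**What to change.** Amend the wording so that Sections 4.1.4, 5.1.1, 5.1.2, 5.2.2.1, 5.3.1 to 5.3.3, 5.4.1, 5.4.2 and 9.2 agree, or state when each applies. In particular:

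1. Give the recovery window for each kind of toxicity and the day it runs from.
2. State which of Sections 5.1.1 and 5.3.2 applies when one neutropenia episode meets both.
3. State how many reductions a patient may have, how that relates to Day 8 omission, and for whom level -2 exists.
4. Use one DLT definition. Say whether the Section 5.1.1 Day 11 event belongs to it and under what attribution, how marrow-involved patients count for haematological DLT in Sections 9.2 and 9.6, and which cycle-delay criterion holds.
5. State which definition was applied to the first six patients, and report aim 1.1.2 and the Section 9.2 excessive toxicity event on the agreed definition.

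The study committee decides which clinical rule applies in each case. The cost is a wording amendment and one statement on how the first six patients were classified; no new data are needed.
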